## 6. Study Procedures

The subjects will be recruited for 5 study visits (Figure 1). After informed, written consent is obtained, subjects will be admitted to the Clinical Research Center (CRC).

[figure not shown]

Figure 5. Study timeline

### Study visit 1:

#### Day 1:

- Subjects will arrive to the CRC after an overnight fast.

- They will undergo standard physical examination; anthropometric measurements (height, weight, waist and hip circumference) perform body composition assessment via DEXA imaging (dual-energy x-ray absorptiometry) will be recorded.
- *Baseline glucose tolerance* will be assessed by an oral glucose tolerance test (OGTT).
- Subjects will be handed a visual analog scale (VAS) questionnaire designed to capture their perceived hunger and satiety sensations, food preferences, cravings, and feeding behavior prior to intervention. The questions will be explained by the researcher and subjects will be instructed to bring in the completed questionnaire on their second visit.
- Subjects will be provided snacks and asked to return to CRC at 7 pm for the nutrient sensing test to be performed the following day. The subject will be fed a standardized meal and restricted to water after 8:00 pm.

## Day 2

- Blood will be drawn for determination of fasting plasma insulin, C-peptide, CBC, CMP, lipid profile, liver enzymes, PT, PTT, and gut hormones including ghrelin, GIP, GLP-1, pancreatic polypeptide (PP) and PYY.
- Subject will then consume a standardized 250 kcal liquid mixed meal containing 40 g carbohydrates, 6 g fat, and 9 g protein (8 oz. Ensure; Abbott Nutrition, Columbus, OH) within 10 minutes. Blood will be drawn at 15, 30, 60, and 120 minutes after consumption following which subject will be discharged.

## Study visit 2 (within 2 weeks after the first visit):

- Subjects will undergo esophagogastroduodenoscopy (EGD) procedure for the delivery of BOTOX to the duodenal wall, to be performed by [name] at the Vanderbilt Gastrointestinal Endoscopy Suite (VGIES). We have been exempted from Investigational New Drug (IND) regulation for the proposed testing by the FDA (letter attached).
- Subjects will be monitored in the VGIES for 30 minutes and discharged with instructions for follow-up and contact information of the physicians' team (Drs. [name], [name]).

**Telemedicine visit** (1 week after SV2): Study team member will contact subject by telephone to assess if there have been any adverse events from the study procedures completed thus far.

**Study Visits 3-5** (1, 3, and 6 months after EGD): On every study visit, body weight, body composition via DEXA, food intake, and feeding behavior will be recorded and post-absorptive OGTT will be performed. Nutrient sensing test will be repeated at visit 3.

## Oral Glucose Tolerance Test (Study visits 1 and 3-5):

- **Day 0:** Subjects will be fasting overnight (and restricted to water only after 8 pm).
- **Day 1:** Blood will be drawn for determining fasting blood glucose levels. At 8:00 am subjects will drink Trutol™ 75 (Thermo Scientific), a solution of 75g dextrose in 300 ml of water in 10 minutes. Blood will be drawn at 15, 30, 45, 60, and 120 min post ingestion.
- The subject will be fed a standardized snack and discharged around noon.

## Endoscopic delivery of BOTOX via EGD (Study Visit 2):

- Subjects will arrive fasted at the GI Suite in the main hospital at Vanderbilt University for the EGD procedure.
- Under the supervision of an anesthesiologist, subjects will be given combination of intravenous medications, so they fall asleep. [name] will then pass the endoscope,

a long, flexible tube with light, video camera and channel for small instruments including syringes through the esophagus and stomach, pylorus into the junction of the 1st and 2nd parts of the duodenum. Botox (100 units dissolved in 200 µL of sterile, preservative-free 0.9% Sodium Chloride, USP) will be injected along the medial (mesenteric) border, into the duodenal muscle wall.

**Post EGD Care:**

- Following completion of EGD procedure and emergence from anesthesia, subjects will be monitored in the VGIES-dedicated post-anesthesia care unit (PACU) prior to discharge.
- Subjects will be provided written instructions regarding potential signs and symptoms of adverse events, including fever, pain, bleeding, and muscle weakness. They will be provided the 24/7 physician call number for any questions or issues that may arise.

**Nutrient sensing test (study visit 1 and 3):**

- **Day 1:** After OGTT subjects return to CRC at 7:00 pm. They will be fed a standardized meal and fasted overnight (restricted to water after 8:00 pm).
- **Day 2:** At 8:00 am, blood will be drawn for determination of fasting plasma insulin, C-peptide, and gut hormones stated above. Subject will then consume a standardized 250 kcal liquid mixed meal containing 40 g carbohydrates, 6 g fat, and 9 g protein (8 oz. Ensure; Abbott Nutrition, Columbus, OH) to be administered over a 10-min period. Blood will be drawn 15, 30, 60, and 120 minutes later. At the end of the study, subject will be provided a standardized meal/snack and discharged.
- All blood samples will be collected in chilled EDTA tubes with protease and DPP IV inhibitors, and immediately centrifuged at 4°C to separate plasma. The MILLIPLEX MAP Human Metabolic Hormone Magnetic Bead Panel (Millipore) will be used to simultaneously assay eight analytes. Cholecystokinin (CCK) will be measured by radioimmunoassay (RIA, ALPCO Diagnostics). Blood for CCK measurement will be collected with 500 KIU Trasylol/1 ml blood. Free fatty acids, cholesterol, and triglycerides will be assayed in the Vanderbilt Diabetes Research and Training Center Lipid Core. Glucose will be measured by the glucose oxidase method using a Beckman Glucose Analyzer.

## 7. Risks

**EGD Procedure-related risk:**

- EGD for delivery of Botox will be performed as per standard protocols and are of little risk to the subject, with minimal chance of bleeding.
- [name] and his group at VGIES have performed over 1000 such endoscopies with the least adverse effects.

**Post EGD Care:** Following completion of EGD procedure and emergence from anesthesia, patients will be monitored in the Vanderbilt GI Endoscopy Suite's (VGIES) dedicated post-anesthesia care unit (PACU) and evaluated by physician and nursing staff prior to discharge. Subjects will be provided written instructions regarding potential signs and symptoms of adverse events, including fever, pain, bleeding, and muscle weakness. They will be provided the 24/7 physician call number for any questions or issues that may arise.

**Drug-related risk:**

- Based on prior clinical trials targeting other neuromuscular disorders, the most commonly reported event following Botox injection is temporary local muscle weakness at the

injection site, and rarely remote tissues occurring as a result of “spread of toxin effect”. Almost all of this has been reported to disappear in about 3-5 days.

- Subjects will be provided handouts providing detailed information on potential adverse events including nausea, muscular weakness, and pain in extremities and injection site.
- Subjects will be instructed to call the 24/7 number if required, for assistance in management and care of any adverse events or discussion of other potential issues.
- A specialized nurse from the VGIES will call the subject at 1 and 7 days post-procedure, and as needed.

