## 3. Animal Studies and Previous Human Studies

### 3.1 Animal Studies

[figure not shown]
We have developed a surgical model for Botox injections in mice. Mice are anesthetized by isoflurane inhalation and laparotomy is performed to expose the intestines. Botox loaded into Hamilton syringes fitted with 30 g needles is injected into the smooth muscle layer of the duodenum at 3 sites, within 3 cm distal to the pyloric sphincter (Fig 1A) ensuring no drug diffusion into the lumen. High-fat (60%) diet induced obese (DIO) mice injected with

**Fig. 1A:** Duodenal injection site. **B:** Weight loss in DIO mice injected with saline or Botox (0.1-3U/kg body weight;  $n=3$ -4 mice)

Botox showed a dose-dependent decrease in body weight between 0.3-3U/kg body weight, and 3U/kg was observed to be the optimal dosage (Fig. 1B). The effects lasted for at least 7 weeks, following which they begin to dwindle and are almost reversed by the end of 10 weeks. Readouts analyzed to determine dosage and effective treatment time include body weight recordings, and protein expression of neurotransmitter, SNAP-25 and smooth muscle contraction marker phospho-myosin light chain 2Ser19 (P-MLCSer19). We also observed distension of the muscle wall and apparent dysmotility within 48 hours of injection that persisted until 6 weeks later. SNAP-25

Hamilton syringes fitted with 30 g needles is injected into the smooth muscle layer of the duodenum at 3 sites, within 3 cm distal to the pyloric sphincter (Fig 1A) ensuring no drug diffusion into the lumen. High-fat (60%) diet induced obese (DIO) mice injected with

**Fig. 2:** Representative WB of SNAP-25 expression in mice (A) kidney, stomach, colon, brain (for comparison) and duodenum injected with saline or Botox, measured 6 weeks later; P-MLCSer19 and total MLC expression (B) in duodenal injection site 1-10 weeks later.

expression at the Botox injection site was lower, suggesting that *Botox induced proteolysis of SNAP-25 (Fig 2A)*. P-MLCSer19, indicator of smooth muscle contraction in the gut was down-regulated also until 6 weeks, following which expression was restored (Fig 2B). These data suggest that Botox blocks smooth muscle contraction in the intestine.

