### **(d) Data Safety Monitoring Plan (DSMP).**

- Our DSMP will focus on performance, safety, and care of participants. [name], Columbia University, and [name], Washington University St. Louis, will serve as the Data Safety Monitoring Board (DMSB) for this study.
- This is a pilot study. The DSMB will meet with the PIs at least 3 times. We are planning to initially enroll 3 patients and have the DSMB look at the efficacy and safety data. This will involve an initial meeting to ratify the DSMB, a meeting after the first patient undergoes EGD, and after 3 patients complete enrollment. The next meetings will be at the end of the first and second years, respectively. Progress reports will indicate patient recruitment status, adverse event occurrence, and summary of data collected. The DMSB will assess safety data including development of local or peripheral muscular weakness, bleeding, inflammation, hospitalizations, and other serious adverse events. Based on safety reports, the DMSB will advise and consent modification or termination of the study protocol or the study if it deems such actions to be warranted. Each meeting will be virtual, via zoom. We will send minutes to DSMB members for review and approval after each meeting.
- Participating subjects will be monitored by the physician and nursing staff of the VGIES PACU after recovering from anesthesia for EGD procedure and evaluated by physician prior to discharge.
- The research coordinator will be required to be present to record any AEs and report to the PI or co-investigators promptly of such events.

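### Scheduled adverse-event contact ends at about day 7, although the protocol's mouse data show duodenal effects to 6 weeks and Section 12 hopes for benefit to 6 months

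*Combined protocol and SAP*

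**What the plan says.** **Risk text (Section 7, Drug-related risk).** The statement opens: "Based on prior clinical trials targeting other neuromuscular disorders, the most commonly reported event following Botox injection is temporary local muscle weakness". It adds that remote tissues are rarely affected, and continues: "Almost all of this has been reported to disappear in about 3-5 days". No other duration is given in that section.

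**The protocol's own duodenal evidence (Section 3.1).** The source is an animal experiment: "We have developed a surgical model for Botox injections in mice". The finding is: "We also observed distension of the muscle wall and apparent dysmotility within 48 hours of injection that persisted until 6 weeks later". A biochemical marker agrees with it: the phosphorylated myosin light chain, described as an "indicator of smooth muscle contraction in the gut was down-regulated also until 6 weeks, following which expression was restored".

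**Expected duration in this trial (Section 12).** The glucose benefit is expected from 1 month and is hoped to hold to 6 months, or for as long as the drug acts on human gut muscle.

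**Scheduled safety contact after discharge.** Section 7 has an endoscopy nurse telephone on days 1 and 7 and when needed. Section 6 has a telephone visit 1 week after the procedure to ask about adverse events. For visits 3-5 (1, 3 and 6 months), Section 6 says: "On every study visit, body weight, body composition via DEXA, food intake, and feeding behavior will be recorded". It adds the OGTT at each of these visits and the nutrient sensing test at visit 3. It lists no adverse-event item.

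**What the monitoring board sees (Section 9(d)).** "The DMSB will assess safety data including development of local or peripheral muscular weakness, bleeding, inflammation, hospitalizations", followed by a residual category of other serious events. Progress reports to the board also include the occurrence of adverse events in general.

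**The concern.** The efficacy case needs an effect on duodenal muscle that lasts weeks to months. The safety text offers only a figure in days, taken from a different tissue in other indications, and scheduled safety contact stops at about the same point. If the drug does act on the human duodenum for as long as the protocol hopes, most of that period falls where no one is instructed to ask about symptoms.

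Two things are at stake. The first is the safety record of a use that Section 1 describes as never explored. Serious events would probably surface anyway, but non-serious vomiting, bloating or distension at week 3 or month 2 may not. Without a uniform question at fixed times, a low count cannot be told apart from a low rate of reporting. The second is interpretation. Section 11 compares measurements before and after treatment, with no control arm. Symptomatic nausea or vomiting could lower weight by an unintended route. Recording food intake would show that intake fell, but not why.

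**Working it through.** The plan states no figure to reproduce. The check sets the passages side by side and adds timeline arithmetic.

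**Do the 3-5 days and the 6 weeks concern the same thing?**

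| | Section 7 | Section 3.1 |
|---|---|---|
| Species | Human | Mouse |
| Site | Muscles treated in other disorders | Duodenal wall |
| Endpoint | Muscle weakness, local or rarely remote | Distension, apparent dysmotility, contraction marker |
| Duration | About 3-5 days, for nearly all of it | Within 48 hours to 6 weeks |

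They differ on every row, so both can be true. In days, 6 weeks is 6 × 7 = 42. That is 42 / 5 = 8.4 to 42 / 3 = 14 times the figure in the risk text.

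**How much of the mouse window has scheduled safety contact?** The last such contact is at about day 7.
- Days left uncovered: 42 − 7 = 35.
- Share: 35 / 42 = 83%.

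**How much of the trial's follow-up comes after that contact?** Assume 30-day months, so that visits 3, 4 and 5 fall at about days 30, 90 and 180.
- Days after the last contact: 180 − 7 = 173.
- Share: 173 / 180 = 96%. A month of 30.4 days also gives 96%.

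**What would a review at visits 3-5 have to cover?** The recall periods would be 30 − 7 = 23 days, 90 − 30 = 60 days and 180 − 90 = 90 days. Visit 3 falls inside the 42-day window seen in mice, and visit 4 is the first visit after it.

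**Is the effect named anywhere in the safety text?** As described in Section 7, the handout covers nausea, muscular weakness and pain. The post-procedure instructions cover fever, pain, bleeding and muscle weakness. The board's list is quoted above. None of them names duodenal dysmotility or its symptoms beyond nausea. Yet gastroparesis is an exclusion criterion in Section 4.

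**The case against.** The strongest defence is that adverse events are already captured. Section 9 grades all of them, including mild ones, and sends an annual summary. Section 9(d) requires the coordinator to record any that arise. The 24-hour number and the as-needed nurse calls have no end date. The handout and board lists are introduced as examples, not as complete lists. Subjects meet study staff in person at 1, 3 and 6 months. Section 3.2 says that reactions generally appear in the first week, which fits contacts on days 1 and 7.

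Much of this stands. A reader might infer that adverse events after day 7 go unrecorded; the documents do not support that. The gap is the lack of a scheduled, uniform question. Nor do the documents say that days 1 and 7 were chosen because of the 3-5 day sentence.

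The first-week statement does not close the gap. It concerns onset in other indications, not how long an effect lasts in the duodenum. The overactive-bladder data in the same section show that longer observation can raise a count: urinary tract infection is 18% within 12 weeks and 26% over the whole study. That 12-week window belongs only to the two bladder tables and should not be read as applying to all the human tables. General recording duties that are tied to no visit leave late, mild symptoms to whoever mentions them.

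A reader might also take reduced motility as a rival explanation for weight loss. It is not one: Section 1 gives blocked contraction of the gut wall as the intended mechanism. Only symptomatic nausea or vomiting could be a rival.

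**Conclusion.** The point holds in a limited form. Section 7 gives one resolution time, from weakness in other indications. The protocol's mouse duodenal data run to 6 weeks, and Section 12 anticipates benefit to 6 months or for the drug's duration of action. No adverse-event assessment is listed after about day 7, which leaves about 173 of 180 days (96%) to spontaneous report and unscheduled recording.

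It is tempting to say that the risk text contradicts the animal data. It does not: the two passages are in tension and need reconciling. Nor is dysmotility the only effect seen in the mouse duodenum. Section 3.1 also reports wall distension, lower SNAP-25 and a reduced contraction marker.

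The 96% assumes 30-day months and a last scheduled contact at day 7. The 83% describes the window in mice; how long duodenal effects last in humans is not known from the documents. The study timeline figure is not shown, the handout is not included and the consent pages were removed. If one of these already sets out an adverse-event review at visits 3-5, the remaining work is to bring Section 6 into line. The weakness does not undermine the design, but it is worth correcting because the remedy is so cheap.

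**What to change.** 1. In Section 6, add a scripted adverse-event review to visits 3, 4 and 5. Ask every subject the same questions about the time since the last contact, including gut-motility symptoms such as nausea, vomiting and abdominal distension. Record onset and resolution dates, and grade on the Section 9 scale. The dates matter because the recall periods are 23, 60 and 90 days.
2. In Section 9(d), state that the results, including non-serious gut symptoms, go to the monitoring board.
3. In Section 7, and wherever the statement is repeated to subjects, reconcile the 3-5 day sentence with Sections 3.1 and 12. Say that it concerns muscle weakness in other indications and that the duration of duodenal effects in humans is unknown.

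The cost is one short form at three visits that already take place, plus the wording changes. Dose, treatment and clinical care are not affected.

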## 8. Protection against risks

### 8.1. Recruitment and Informed Consent

- Subjects will be recruited via solicitation flyers, Research Match, LISTSERV, advertisements, and Facebook posts listing study objectives and design, inclusion criteria, remuneration, and contact information.
- Recruitment email will be sent using Vanderbilt’s “Research Notification” list that reaches all Vanderbilt employees and can therefore target a large population.
- In addition, census lists from the Vanderbilt Center for Surgical Weight Loss will be screened for eligible candidates, based on inclusion/exclusion criteria. Subjects who do not qualify for bariatric surgery, or subjects who are awaiting insurance approval for a bariatric procedure will be contacted via emails and telephone calls.
- Interested subjects will attend a pre-study seminar session entailing the study’s purpose, procedures, and potential risks. If subjects are still interested they will be directed to contact the recruiter for more information and additional screening. During the screening the recruiter will further review inclusion and exclusion criteria and explain the study procedures, duration of the study, benefits of participation, and potential risks, and answer any remaining questions.
- If the subject indicates interest, a copy of the informed consent will be provided (by hand, mail, or email); time will be allowed for the subject to read through the form and ask additional questions or express concerns.
- Subjects will sign the consent at the time of their screening visit to the Vanderbilt CRC. Signed consent forms will be uploaded to a secure password-protected REDCap® (Research Electronic Data Capture) database.

### 8.2. Protections against risk

(a) Minimizing physical, psychological, and social risks. Participation in this study is completely voluntary. Subjects will be free to drop out of the study due to any issues related, but not limited to physical discomfort, pain or other adverse events (AEs). Screening will be performed by a physician or nurse staff to ensure appropriate selection criteria are employed. Subjects will be free to refuse to respond to any question that may result in psychological disturbance. All patient care information utilized will be confidential and anonymous.

(b) Minimizing risks to confidentiality.

- All records and data will be de-identified and securely stored in Vanderbilt’s HIPAA-compliant, password protected data base, REDCap®; this is a secure web application for collection and management of clinical trial data developed by Vanderbilt University in collaboration with a vast consortium of thousands of active institutional partners.
- The subject’s identification is concealed, and a number is used as the identifier instead of the name. Only the PI, co-investigator, and research assistant will have access to identifiable private information. The PI will be responsible for maintaining the repository

and the identity of the samples. De-identified specimens will be released by the PI to projects after IRB approval only. Any paper documents will be stored in the PI's locked officer. All research samples (serum and plasma) obtained will be de-identified and stored in our locked freezers for an unlimited period of time. Only research personnel associated in our laboratory who are directly involved with the study will have access to research samples.

## **9. Reporting of Adverse Events or Unanticipated Problems involving Risk to Participants or Others**

Should a study-related adverse event (AE) result in harm or injury, neither the subject nor their insurance company will be responsible for the cost of immediate medical care provided at Vanderbilt to treat the injury. There are no plans for Vanderbilt to pay for the costs of any additional care.

***Adverse Event Reporting:*** All AEs will be graded according to the following scale:

- 0 = No adverse events or within normal limits
- 1 = Mild; did not require treatment
- 2 = Moderate; resolved without treatment
- 3 = Severe; required professional medical attention
- 4 = Life-threatening or disabling
- 5 = Death

All unanticipated, serious AEs related to the experimental procedures that are Grade 1 or above will be reported immediately to the DSMO (see below) and within 1 day to the IRB. The PIs will review AEs and notify the IRB and NIDDK of any changes needed to the protocol. The annual summary of all adverse events and any audit reports will be sent to the NIH and IRB at the time of continuing review.

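### The adverse-event scale mixes intensity with treatment and outcome, so a moderate event that needed treatment, or an untreated one that has not resolved, fits no grade

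*Combined protocol and SAP*

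**What the plan says.** Section 9 makes one scale compulsory: "All AEs will be graded according to the following scale". Its lower and middle grades read:

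- where nothing has happened, "0 = No adverse events or within normal limits"
- for the lowest grade of actual event, "1 = Mild; did not require treatment"
- for the grade above it, "2 = Moderate; resolved without treatment"
- for the third grade of event, "3 = Severe; required professional medical attention"
- for the last grade short of a fatal event, "4 = Life-threatening or disabling"

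Grade 5 is death. No other part of the document defines mild, moderate or severe, and no second scale is given.

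The grade appears once more in Section 9, in the rule for rapid reporting: "All unanticipated, serious AEs related to the experimental procedures that are Grade 1 or above will be reported immediately to the DSMO". The same section promises the NIH and the IRB a yearly summary of adverse events. The Data Safety Monitoring Plan, also in Section 9, says of the DSMB's material: "Progress reports will indicate patient recruitment status, adverse event occurrence, and summary of data collected".

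**The concern.** A severity scale should give every event exactly one grade, on one dimension. This scale uses three: an intensity word in grades 1 to 3, a treatment or care condition in grades 1 to 3, and an outcome (resolution) in grade 2 only. Where these disagree, the assessor must ignore either the label or the condition, and the protocol does not say which.

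What is at stake is the severity record of a small study that describes its use of the drug as unexplored. Two assessors could grade the same treated, moderate event differently while both follow the text. One would keep it at grade 2 for its intensity, and the other would move it to grade 3 because care was needed.

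**Working it through.** No figure is involved, so the check is a logical one: are grades 1 to 3 mutually exclusive and exhaustive for events that are neither life-threatening, disabling nor fatal? The inputs are the grade definitions in Section 9, read literally.

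**Step 1. Cross intensity with treatment and outcome.**

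| Event | Grade 1 | Grade 2 | Grade 3 | Result |
|---|---|---|---|---|
| Mild, no treatment needed, resolved | label and condition met | condition met, label not | no | Grade 1, by label only |
| Moderate, no treatment, resolved | condition met, label not | label and condition met | no | Grade 2, by label only |
| Moderate, no treatment, not resolved | condition met, label not | label met, resolution not | no | No grade |
| Moderate, treatment needed but no professional care | no | label met, condition not | no | No grade |
| Moderate, professional care needed | no | label met, condition not | condition met, label not | No grade, unless called severe |
| Severe, professional care needed | no | no | label and condition met | Grade 3 |

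**Step 2. Overlap.** In the first two rows the event meets the treatment condition of both grade 1 and grade 2. The conditions differ in wording (treatment not required, as against resolved without it), but an event that resolves untreated will ordinarily satisfy both. Only the undefined labels then decide.

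**Step 3. Gaps.** Three of the four moderate rows have no matching grade. Mild events are left out of this count. Grade 1 asks whether treatment was required, so a mild event for which a subject chose to take something can still be grade 1.

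**Step 4. Are the gaps foreseeable?** Section 7, under drug-related risk, lists nausea, weakness, and pain in the limbs or at the injection site. It also gives subjects a round-the-clock number for help with any event, not only a severe one. Treated, moderate events are therefore to be expected. The resolution gap can also arise on the protocol's own timetable. Section 7 says that almost all of the muscle weakness clears in about 3 to 5 days, and schedules a nurse call at day 1. Weakness that begins at the procedure and lasts 3 to 5 days is still present at that call. If it is moderate and untreated, grade 2 cannot yet be assigned.

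**Step 5. Where do the grades go?**

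- *Rapid reporting.* The rule requires an event to be unanticipated, serious, related and grade 1 or above. Grade 0 means no event, so the grade condition admits every event. Moving an event among grades 1, 2 and 3 changes no report.
- *Efficacy and power.* Section 11 covers body weight, gut-peptide AUC and glucose AUC, and analyses no adverse events. Nothing there depends on a grade.
- *Summaries.* Any severity breakdown in the yearly summary or the DSMB reports would have to come from this scale, because there is no other.

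**The case against.** The best case for leaving the scale alone is that the labels do the work. Mild and moderate are different words, clinicians grade by judgement everywhere, and the phrases after the semicolons can be read as loose illustrations. Nothing decisive depends on the grade, and with 20 subjects the DSMB can look at each event by name. Much of this stands, and it limits the point. It does not close the gaps: Section 9 does not present the conditions as illustrations, and read as written they contradict the label for a treated moderate event.

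Four stronger readings are tempting, and the documents do not support them.

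- *Grades 1 and 2 cannot be told apart.* They can, by label. The fault is that the labels are undefined and the stated conditions overlap.
- *Any event seen by a clinician becomes severe.* Grade 3 says that professional attention was required, and it carries the label severe. Staff see every subject after the endoscopy, and a nurse telephones every subject at days 1 and 7. The protocol does not treat such contact, or a call to the physician line, as grade 3.
- *The scale distorts expedited reporting.* It does not, for the reason given in the last step of the check.
- *The DSMB will be misled.* The monitoring plan promises the board the occurrence of events and directs it to named ones: muscle weakness, bleeding, inflammation, hospital admissions and other serious events. No pausing or stopping rule uses a grade. A severity profile may reach the board, but the plan does not say that it will.

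**Conclusion.** The point holds as a defect in a stated rule. The scale is compulsory for all adverse events, yet it has no grade for a moderate event that needed treatment, or for a moderate untreated event that has not resolved, unless either is called severe. Grades 1 and 2 are separated only by undefined words. The severity recorded for the events that the protocol itself expects would depend on how each assessor resolves the conflict.

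The number of events affected cannot be calculated, because the documents give no expected rate of treated, moderate events for this injection site. For scale only: if severity were tabulated by subject, one misgraded subject would be 1/20 = 5% of the planned sample, or 1/3 = 33% at the planned DSMB review of the first 3 patients.

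The conclusion rests on reading the definitions as written and on there being no definition of the labels elsewhere in the document. It reaches the recorded severity and any severity reporting to the NIH, IRB and DSMB, and goes no further. It should be corrected because the correction is cheap, not because the validity of the trial depends on it.

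**What to change.** Reword grades 1 to 3 in Section 9 and on the adverse-event form so that every event fits exactly one grade by intensity, with mild, moderate and severe each defined. Adopting an established published severity scale would do this without new drafting. Remove resolution from grade 2. Record the treatment given and the outcome as separate fields, so that this information is kept but no longer decides the grade. Grades 0, 4 and 5 can stay as they are, unless a published scale replaces the whole list.

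The cost is a few lines of protocol text and two fields on the form. Any events already graded on the present wording would need to be regraded, so that the summaries use one scale throughout.
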